8.3 Analysis Sets

The following analysis sets will be defined:

Full Analysis Set

The FAS will include all subjects who received any amount of IMP.

Primary Efficacy Analysis Set

The Efficacy Analysis Set will include subjects in the FAS who were no older than 8 months of age on the date of the first infusion of sebelipase alfa.

PK Analysis Set

The PK Analysis Set will include all available sebelipase alfa serum concentration data for subjects who received at least one complete infusion of IMP in this study.

Per Protocol Analysis Set

The Per Protocol Set (PPS) will include subjects in the Primary Efficacy Analysis Set who, in addition, receive at least 4 complete infusions of sebelipase alfa. This set will be used for sensitivity analyses of efficacy endpoints.

8.4 Demographics and Baseline Characteristics

Demographics and baseline characteristics will be listed for each subject and tabulated. Chronological age will be reported in months to one decimal (xx.x months).

8.5 Subject Accountability

Data from all subjects who are enrolled (i.e., treated) in the study will be included in the summary of subject accountability. The frequency and percentage of subjects who are enrolled in the study, discontinued from the study, and completed the study, along with reasons for discontinuation, will be summarized.

8.6 Study Treatment Usage and Compliance

Number of weeks in the study and number of study infusions received by subjects will be summarized. The number (percent) of subjects who receive all study infusions 'per protocol' (i.e., subjects without missed infusions or infusion interruptions or rate changes) will be provided. A listing will be provided that summarizes sebelipase alfa exposure by subject, and date of first dose and total number of doses (by dose level) of sebelipase alfa under study LAL-CL03.

8.7 Efficacy Analysis

Efficacy will be analyzed for the Primary Efficacy Analysis Set. If the PPS is not identical to the Primary Efficacy Analysis Set (i.e., if at least one patient in the Primary Efficacy Analysis Set is excluded from the PPS), efficacy analyses will be repeated for the PPS.

The primary efficacy endpoint is the proportion of subjects surviving to 12 months of age. It is not anticipated that any subjects will be lost to follow-up prior to 12 months of age, but a subject who is not confirmed to have survived to 12 months of age will not be considered to have met the primary endpoint. As a complementary analysis, Kaplan-Meier survival curves of survival since birth and survival since first dose of IMP will be presented.

Survival at 18 and 24 months of age will be analyzed as described for the primary endpoint. Median age at death will also be calculated. A Kaplan-Meier estimate of median survival past first dose of IMP will be computed.

Estimated survival rates and median age at death derived from this study will be compared to rates/times reported in the literature, and will be discussed in conjunction with information derived from a natural history study in a similar patient population (study LAL-1-NH01).

Anthropometric indicators of growth, standardized by age and gender in accordance with the methodology described by the WHO and using WHO growth charts will be listed by study time point as observed values and as changes from baseline. Change from baseline in anthropometric data will be tabulated as continuous data. In addition, the percentages of subjects who meet criteria for underweight, stunting, and wasting will be tabulated for each timepoint. For anthropometric indicators of growth, age will be adjusted for prematurity if gestational age is <37 weeks and the subject is under 12 months of age. The adjustment will be made such that corrected age = chronological age minus the number of months premature.

Change and/or percent changes from baseline in AST, ALT, and serum ferritin will be tabulated for each evaluation timepoint.

A subject will be considered to have achieved transfusion-free hemoglobin normalization (TFHN) if the subject meets all of the following criteria:

- 1. Has two post-baseline measurements of hemoglobin at least 4 weeks apart that are both above the age-adjusted lower limit of normal (LLN);
- 2. Has no known additional measurements of hemoglobin that are below the age-adjusted LLN during the (minimum) 4-week period; and

Page 58 of 76

3. Had no transfusions during the (minimum) 4-week period, and also no transfusions for 2 weeks prior to the first hemoglobin measurement in the (minimum) 4-week period.

If all 3 criteria are met, the subject will be considered to have achieved TFHN on the date of the first hemoglobin assessment in the 4-week period. The proportion of subjects who achieve TFHN will be summarized and, if sufficient data are available, a summary of time to TFHN will be created.

A subject who is transfusion-free beginning at Week 6 will be considered to have maintained transfusion-free normal hemoglobin if, regardless of baseline hemoglobin value, the subject has no abnormally low hemoglobin values beginning at Week 8 of the study and continuing for at least 13 weeks (3 months). The proportion of subjects who have maintained transfusion-free normal hemoglobin will be summarized.

The Denver II total score and functional area scores will be derived from the questionnaire in accordance with the Technical Manual and compared to appropriate demographic norms. The total score and functional area scores will be summarized as continuous data and according to the classification as to whether the subject displays abnormal/normal development (Polat, 2010, *Pediatr Int*).

Shift tables will be used to tabulate dietary changes, including discontinuation of a low-fat/lowcholesterol diet and/or introduction of an unrestricted age-appropriate diet. Observed values and changes and/or percent changes from baseline in other exploratory efficacy endpoints will be tabulated for each evaluation timepoint.

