3.1 Overview of Study Design and Flow Chart

This is an open-label, repeat-dose, dose escalation study of sebelipase alfa in children with growth failure due to LAL Deficiency. Eligible subjects will receive IV infusions of sebelipase alfa for up to 5 years, as described below. All subjects will be evaluated for safety, tolerability, and efficacy. Where feasible, given blood volume thresholds based on subject weight, blood samples will also be collected for analyses of the PK and PD of sebelipase alfa and for an exploratory analysis of potential disease-related biomarkers in this patient population.

All subjects will initiate treatment with sebelipase alfa at a dose of 0.35 mg/kg qw. After receiving 2 infusions at this starting dose, a subject will receive a dose increase to 1 mg/kg qw, contingent upon acceptable safety and tolerability of preceding infusions. A further dose escalation to 3 mg/kg qw may be considered for a subject who has received at least 4 infusions at a dose of 1 mg/kg qw, and meets the criteria for dose escalation defined in Section 3.1.1, contingent upon acceptable safety and tolerability of preceding infusions.

An independent safety committee will oversee safety in this study. The SC will review available safety data for each subject (1) following the first 2 infusions at a dose of 0.35 mg/kg qw to determine the acceptability of escalating the dose to 1 mg/kg qw and (2) following the first 2 infusions at a dose of 1 mg/kg qw to determine the acceptability of continuing treatment at this dose level. In addition, for subjects who are escalated to a dose of 3 mg/kg qw, the SC will review their safety data following the first 2 infusions at a dose of 3 mg/kg qw to determine the acceptability of continuing treatment at this dose level. The remainder of the safety data for all subjects will be reviewed during at least biannual periodic meetings of the SC and on an ad-hoc basis as needed in the event of unanticipated safety findings.

If the SC does not approve a subject's dose escalation from 0.35 mg/kg qw to 1 mg/kg qw, but deems it safe for the subject to continue treatment at the starting dose of 0.35 mg/kg qw, the subject may continue to receive this starting dose. Re-evaluation of dose escalation will be considered after subsequent SC review and discussion with Sponsor.

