5.1.12 Denver II Developmental Screening Test

The Denver II will be administered at the timepoints specified in Appendix A.

The Denver II is a standardized measure to assess development in children from 1 month to 6 years of age (Frankenberg, 1992, *Pediatr*). The Denver II includes performance-based and parent-reported items in 4 functional areas: fine motor-adaptive, gross motor, personal-social, and language skills. The test was normed on a diverse sample of children who were full term and had no obvious developmental disabilities; the norms indicate when 25%, 50%, 75%, and 90% of children passed each item. The Denver II has good inter-rater and test-retest reliability (correlations \geq 0.90 for most tests).

The Denver II must be administered by a trained clinician and takes an average of 10 to 20 minutes to complete. Administration and scoring of the Denver II is based upon the child's age. (Note that for premature infants, the number of months premature is subtracted from the infant's chronological age.) For each test item administered, the clinician determines if the child's response falls within or outside of the normal expected range of success on that item for the child's age. The interpretation of the individual test items is then used to classify the child's development in each functional area and for the overall test.

Page 41 of 76

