8.1 General Considerations

All data will be presented in listings, and summary tables and/or graphs will be provided, as appropriate. Unless otherwise noted, all tabulations for efficacy endpoints will be presented for subjects in the Primary Efficacy Analysis Set and tabulations for other endpoints will be presented for subjects in the Full Analysis Set (FAS). Descriptive summary statistics (n, mean, median, standard deviation, minimum and maximum) will be calculated for the continuous variables. Shift tables and/or frequencies and percentages will be produced for the categorical variables. When percentages are reported, the number of treated subjects will be used as the denominator. As noted, 95% two-sided confidence intervals (CIs) will be calculated around the estimates based on the exact binomial distribution for binomial endpoints and the t-distribution for continuous endpoints.

Baseline will be defined as the last measurement prior to the first infusion of sebelipase alfa. (Note: For exploratory analyses, the first available measurement after initiation of treatment may be used as baseline if a pretreatment measurement is unavailable.) Survival rates will be based on the age of the subject. Other endpoints, unless otherwise noted, will be based on exposure (i.e., duration of time since the first infusion of sebelipase alfa).

Details of the planned analyses and statistical methodologies will be provided in a separate Statistical Analysis Plan (SAP).

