For anthropometric indicators of growth, age will be adjusted for prematurity if gestational age is <37 weeks and the subject is under 12 months of age. The adjustment will be made such that corrected age in months = chronological age in months minus the number of months premature.

Change and percent change from baseline in AST, ALT, and serum ferritin will be tabulated for each evaluation timepoint.

A subject will be considered to have achieved transfusion-free hemoglobin normalization (TFHN) if the subject meets all of the following criteria:

- 1. Has two post-baseline measurements of hemoglobin at least 4 weeks apart that are both above the age-adjusted lower limit of normal (LLN);
- 2. Has no known additional measurements of hemoglobin that are below the ageadjusted LLN during the (minimum) 4-week period; AND
- 3. Had no transfusions during the (minimum) 4-week period, and also no transfusions for 2 weeks prior to the first hemoglobin measurement in the (minimum) 4-week period.

If all 3 criteria are met, the subject will be considered to have achieved TFHN on the date of the first hemoglobin assessment in the 4-week period. The proportion of subjects who achieve TFHN will be summarized and, if sufficient data are available, a summary of time to TFHN will be created.

A subject who is transfusion-free beginning at Week 6 will be considered to have maintained transfusion-free normal hemoglobin if, regardless of baseline hemoglobin value, the subject has no abnormally low hemoglobin values beginning at Week 8 of the

study and continuing for at least 13 weeks (3 months). The proportion of subjects who have maintained transfusion-free normal hemoglobin will be summarized.

Denver II scores will be summarized with the number of patients who had the test done and tested 'normal', 'suspect', 'untestable' by visit for each of the categories. Additionally this data will be listed.

Shift tables may be used to tabulate dietary changes, including shift from low-cholesterol diet to unrestricted diet if sufficient data exist for summary.

Observed values and changes and percent changes from baseline in other exploratory efficacy endpoints will be tabulated for each evaluation time point. These will include changes in

- o alkaline phosphatase
- o gamma glutamyltransferase (GGT)
- o albumin
- o direct (conjugated), indirect (unconjugated), and total bilirubin levels;

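### Prematurity correction stops at 12 months while the baseline stays corrected, so later change scores for age-indexed growth z-scores in any preterm subject mix two age scales

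*Protocol*

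**What the plan says.** Protocol Section 8.7 states that for anthropometric indicators "age will be adjusted for prematurity if gestational age is <37 weeks and the subject is under 12 months of age", with "corrected age = chronological age minus the number of months premature". The synopsis gives the same rule, and SAP Section 9.1 repeats it with "corrected age in months = chronological age in months minus the number of months premature".

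Three other provisions determine how the rule works in practice:

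- Protocol Section 8.1: "Baseline will be defined as the last measurement prior to the first infusion of sebelipase alfa". Baseline is therefore one fixed value per subject.
- Protocol Section 8.3: the Primary Efficacy Analysis Set holds treated subjects who were "no older than 8 months of age on the date of the first infusion of sebelipase alfa".
- Protocol Section 8.7: "Change from baseline in anthropometric data will be tabulated as continuous data". The percentages underweight, stunted and wasted are also tabulated at each timepoint.

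Follow-up is long: "Eligible subjects will receive IV infusions of sebelipase alfa for up to 5 years" (Protocol Section 3.1). Neither document recomputes baseline after the switch, continues the correction, or plans a sensitivity analysis on age basis. SAP Section 13, which lists departures from the protocol's analyses, does not mention the rule.

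**The concern.** A change score is interpretable only if both of its terms are measured on the same scale. Here a preterm subject's baseline is scored against the reference for a younger (corrected) age, and later values against the reference for the chronological age. The reference median rises with age, so dropping the correction lowers the z-score of an unchanged measurement. A child who tracks a constant corrected z-score would appear to lose ground at the first birthday.

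Underweight and stunting are defined by a cut at -2 SD, and growth failure is the usual entry criterion. Subjects may therefore lie near the cut and cross it for this reason alone.

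Growth z-scores are secondary endpoints, and Protocol Section 3.2.2.1 treats better growth as a precondition for a survival benefit. In the long-term tables the artefact could be read as a waning growth response.

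**Working it through.** The plan states no figure on this point, so there is none to reproduce.

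**Which comparisons mix scales.** A preterm subject in the efficacy set has a baseline at 8 months or younger, which is corrected. A visit under 12 months is also corrected, so that change is consistent. A visit at or after 12 months is uncorrected, so that change is mixed. Subjects first dosed at 12 to 24 months are uncorrected at both times. Weight-for-length/height and wasting do not use age.

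**When the switch occurs.** Growth timepoints run from first infusion (Protocol Section 8.1). With the SAP's month length (Section 7.2), the study week at 12 months of age is (12 - age at first dose) x 30.4375 / 7:

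- first dose at 1 month: week 47.8
- 3 months: week 39.1
- 6 months: week 26.1
- 8 months: week 17.4

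One study-week column can therefore hold corrected values for one preterm subject and uncorrected values for another.

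**Size of the step.** SAP Table 1 gives Z = ((X/M)^L - 1)/(L x S), or ln(X/M)/S when L = 0. The L, M and S values are not in the documents. I assumed:

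| | Monthly rise in median (g) | S | L |
|---|---|---|---|
| Weight-for-age | 1.5-3% | 0.10-0.13 | 0 |
| Length-for-age | 1.2-1.8% | 0.03-0.04 | 1 |
| Head circumference-for-age | 0.4-0.8% | 0.025-0.03 | 1 |

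Corrected z was set between -3 and 0, with S equal at the two ages. For m months premature the median rises by a factor (1+g)^m, so the step is:

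- L = 0: -m x ln(1+g)/S
- L = 1: -(1 + S x z) x (1 - (1+g)^-m)/S

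| | 1 month premature | 2 months premature |
|---|---|---|
| Weight-for-age | -0.11 to -0.30 | -0.23 to -0.59 |
| Length-for-age | -0.26 to -0.59 | -0.52 to -1.17 |
| Head circumference-for-age | -0.12 to -0.32 | -0.24 to -0.63 |

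The step stays negative if S differs by up to 2% between the two ages. Mid-upper arm circumference was not computed.

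**One subject, two months premature, constant corrected z of -2.** On one age basis the change is 0. Under the plan's rule:

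- Weight-for-age (g = 2%, S = 0.115): -2 x 0.0198/0.115 = -0.34
- Length-for-age (g = 1.5%, S = 0.035): -0.93 x (1 - 1/1.0302)/0.035 = -0.78

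**Status flip.** With the same length inputs and corrected z = -1.5, the step is -0.9475 x 0.02934/0.035 = -0.79. The child moves to about -2.29 and becomes stunted with no change in growth.

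**Group mean.** One such subject among 8 moves the mean change by -0.34/8 = -0.04 (weight) and -0.78/8 = -0.10 (length).

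**The case against.** The case for leaving the rule alone has several parts.

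- **Reach.** Protocol Section 8 draws all formal conclusions from the analysis done once every subject has reached 12 months of age, died or withdrawn. The report of that analysis (Protocol Section 12) covers data through 12 months of age. In that window a preterm subject is corrected at baseline and at essentially every visit. The step falls mainly on the final analyses, which Section 8 calls supportive. This stands, and a reader who inferred that the formal growth conclusions are distorted would go beyond the documents.
- **Occurrence.** The documents do not say that any subject was born before 37 weeks. With none, the effect is zero. This stands.
- **Importance.** No hypothesis tests are planned (Protocol Section 8.11.1), no decision depends on a growth z-score, and the secondary endpoints are not ranked. This stands.
- **Visibility and direction.** Individual values are listed, and the bias cannot manufacture a benefit. Both are true, but a conservative bias still gives a wrong estimate, and the tabulated means and percentages would carry it.
- **Reading.** If under 12 months referred to age at baseline, there would be no switch. The natural reading is age at each measurement; the wording would need clarifying either way.

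A reader might also cite Protocol Section 5.1.12, where for the Denver II "the number of months premature is subtracted from the infant's chronological age" with no age limit, as an internal contradiction. It is not one. That section describes a separate instrument, Section 8.7 refers its scoring to a technical manual, and silence about an upper age does not show that none applies.

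**Conclusion.** The rule as written gives a wrong change score for any preterm efficacy-set subject from 12 months of age, and nothing in either document repairs it. It affects weight-for-age and length/height-for-age throughout later follow-up. It affects head and mid-upper arm circumference only up to Week 96, their last scheduled measurement (Protocol Appendix A, Table 2). The underweight and stunting indicators are also affected. The primary survival endpoint is not.

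The direction follows from the z-score formula and a rising reference median. The sizes rest on the assumed growth inputs and apply near 12 months; the step shrinks later as growth slows. A reader might take the length figures as typical of all the growth measures, but length is the most sensitive of the three computed, and weight and head circumference move by roughly half as much. Nor do the documents support treating correction at every visit for up to 5 years as the only valid main analysis. The defect is the mismatch between the two terms, not the 12-month limit itself.

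This is a modest but real flaw in supportive, descriptive tables, worth correcting because the correction is cheap.

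**What to change.** State in SAP Section 9.1 that both terms of every change score use the same age basis. Either of two rules would do this:

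- for visits at or after 12 months, recompute the preterm subject's baseline z-score on chronological age; or
- continue the correction to a stated later age, with any switch at that age handled so that both terms still match.

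Apply the same basis to baseline and follow-up underweight and stunting status wherever they are compared, and show the other basis as a sensitivity analysis.

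In the same edit, say that the 12-month limit is judged on chronological age at each measurement, and define the reference week for months premature. For a birth at 36 weeks the correction is 4 x 7/30.4375 = 0.92 months against 40 weeks, but 1 x 7/30.4375 = 0.23 months against 37 weeks.

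The cost is one extra derived variable and a repeated table. No new data are needed: date of birth and birth history are collected at screening, and the existing rule already requires gestational age.

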The primary efficacy endpoint is the proportion of subjects surviving to 12 months of age. It is not anticipated that any subjects will be lost to follow-up prior to 12 months of age, but a subject who is not confirmed to have survived to 12 months of age will not be considered to have met the primary endpoint. As a complementary analysis, Kaplan-Meier survival curves of survival since birth and survival since first dose of IMP will be presented. Survival at 18 and 24 months of age will be analyzed as described for the primary endpoint. Median age at death will also be calculated. A Kaplan-Meier estimate of median survival past first dose of IMP will be computed. Estimated survival rates and median age at death derived from this study will be compared to rates/times reported in the literature, and will be discussed in conjunction with information derived from a natural history study in a similar patient population (study LAL-1-NH01).

Anthropometric indicators of growth, standardized by age and gender in accordance with the methodology described by the WHO and using WHO growth charts, will be listed by study time point as observed values and as changes from baseline. Change from baseline in anthropometric data will be tabulated as continuous data. In addition, the percentages of subjects who meet criteria for underweight, stunting, and wasting will be tabulated for each timepoint. For anthropometric indicators of growth, age will be adjusted for prematurity if gestational age is <37 weeks and the subject is under 12 months of age. The adjustment will be made such that corrected age equals the chronological age minus the number of months premature.

Change and/or percent changes from baseline in AST, ALT, and serum ferritin will be tabulated for each evaluation timepoint. The proportion of subjects with abnormal hemoglobin at baseline who achieve transfusion-free hemoglobin normalization (TFHN) will be summarized, as will the proportion of subjects who maintain transfusion-free normal hemoglobin.

The Denver II total score and functional area scores will be derived from the questionnaire in accordance with the Technical Manual and compared to appropriate demographic norms. The total score and functional area scores will be summarized as continuous data and according to the classification as to whether the subject displays abnormal/normal development.

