2.2.2 Secondary Endpoints

Secondary efficacy endpoints are:

- proportion of subjects surviving at 18 and 24 months of age;
- median age at death;
- changes from baseline in percentiles and/or z-scores as determined from WHO criteria for
 - o Weight-for-Age (WFA),
 - o Weight-for-Length (WFL) and/or Weight-for-Height (WFH),
 - o Length-for-Age (LFA) and/or Height-for-Age (HFA)
 - o head circumference-for-age (HCFA)
 - o mid-upper arm circumference-for-age (MUACFA);
- dichotomous growth status indicators of underweight, wasting, and stunting.
- changes from baseline in
 - o alanine aminotransferase (ALT)
 - o aspartate aminotransferase (AST)
 - o serum ferritin
- normalization of hemoglobin levels without requirement for blood transfusion;

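### Protocol 8.7 and SAP 9.1 omit the synopsis's restriction of TFHN to infants with abnormal baseline hemoglobin, so an infant who starts and stays normal counts as normalized

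*Protocol*

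**What the plan says.** SAP 2.2.2 lists "normalization of hemoglobin levels without requirement for blood transfusion" among the secondary efficacy endpoints, as does Protocol 3.2.2.1. The protocol describes the summary in two ways.

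- **Synopsis, statistical plan, efficacy:** "The proportion of subjects with abnormal hemoglobin at baseline who achieve transfusion-free hemoglobin normalization (TFHN) will be summarized".
- **Protocol 8.7, repeated in SAP 9.1:** a subject achieves TFHN on meeting three criteria. In short: two post-baseline hemoglobin values above the age-adjusted lower limit of normal (LLN), at least 4 weeks apart; no known value below the LLN in between; and no transfusion in that window or in the 2 weeks before its first value. The date of achievement is the date of that first value. Then: "The proportion of subjects who achieve TFHN will be summarized".

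The denominator is left to the general rules. Protocol 8.1 says "When percentages are reported, the number of treated subjects will be used as the denominator". SAP 7.1 uses everyone in the relevant population as a general default, unless something else is specified.

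The next paragraph of Protocol 8.7 and of SAP 9.1 defines a second endpoint, maintained transfusion-free normal hemoglobin. That definition applies "regardless of baseline hemoglobin value". The phrase is not attached to TFHN.

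**The concern.** None of the three criteria looks at the baseline value. An infant whose hemoglobin is normal before the first infusion, and who simply stays normal and untransfused, satisfies all of them. That infant had nothing to normalize, yet would be counted as a success on an endpoint named for normalization.

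A programmer working from the SAP would build the unrestricted version, while a reader of the synopsis would expect the restricted one. With about 8 subjects each infant is worth 12.5 percentage points (1/8), so the choice of population can visibly change the reported proportion. Time to TFHN is also affected, because a baseline-normal infant can be dated as normalizing at the first post-baseline measurement.

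**Working it through.** **Text check.** The places that could settle the population, side by side:

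| Place | Baseline condition on TFHN |
|---|---|
| Protocol synopsis, efficacy analysis | Abnormal hemoglobin at baseline |
| Protocol 8.7, three criteria and summary sentence | None |
| SAP 9.1, three criteria and summary sentence | None |
| Protocol 8.1, SAP 7.1 (default denominators) | None; all subjects in the set |
| SAP 13 (changes from protocol) | TFHN not mentioned; only the Denver II total score |
| SAP Summary of Amendments | TFHN not mentioned |

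The SAP was written against an earlier protocol amendment, but that does not explain the difference: the synopsis and Section 8.7 belong to the same protocol.

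**One infant through the rule.** Baseline hemoglobin is normal, every later value is above the LLN, and there are no transfusions. Criteria 1, 2 and 3 are all met. TFHN is achieved, and the date can be that of the first post-baseline value.

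**Size.** The plan states no TFHN rate or target, so there is no figure of its own to reproduce. The only input from the documents is the planned Primary Efficacy Analysis Set of about 8 (Protocol 8.2). The number of baseline-normal infants is not given; I assume 0 to 4.

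Let k = infants normal at baseline, k′ = those of them who meet TFHN, and r = baseline-abnormal infants who meet TFHN.

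- Unrestricted rate (Protocol 8.7, SAP 9.1): U = (r + k′)/8
- Restricted rate (synopsis): R = r/(8 − k)
- For k ≥ 1, difference: U − R = (k/8) × [k′/k − r/(8 − k)]

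U therefore exceeds R only when baseline-normal infants meet TFHN at a higher rate than the others.

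| k | k′ | r | U | R | U − R (points) |
|---|---|---|---|---|---|
| 0 | 0 | 4 | 4/8 = 50.0% | 4/8 = 50.0% | 0 |
| 1 | 1 | 3 | 4/8 = 50.0% | 3/7 = 42.9% | +7.1 |
| 2 | 2 | 3 | 5/8 = 62.5% | 3/6 = 50.0% | +12.5 |
| 3 | 3 | 2 | 5/8 = 62.5% | 2/5 = 40.0% | +22.5 |
| 4 | 4 | 2 | 6/8 = 75.0% | 2/4 = 50.0% | +25.0 |
| 2 | 0 | 3 | 3/8 = 37.5% | 3/6 = 50.0% | −12.5 |

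The extremes over k = 0 to 4 are +50 points (k = 4, k′ = 4, r = 0) and −50 points (k = 4, k′ = 0, r = 4). If every infant meets TFHN, both rates are 100%. For the row k = 2, k′ = 2, the exact 95% intervals (Clopper-Pearson) are 24.5% to 91.5% unrestricted and 11.8% to 88.2% restricted.

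**The case against.** The best defence is that the intention is already clear. The synopsis states the restriction, the word normalization implies a starting abnormality, and the disregard of baseline is written only for the companion endpoint. On this view it is a harmonization gap. That stands as a description of the cause. It does not remove the gap, because the operative text in SAP 9.1 lacks the restriction and the defaults do not restore it.

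A second defence is that little depends on it. Protocol 8.11.1 plans no formal testing, time to TFHN is produced only if the data suffice, all data are listed, and SAP 10.2 plots hemoglobin by subject (the amendment summary drops only the change plots). A careful reader could see who started normal. This limits the consequence. But when an endpoint is purely descriptive, the proportion is the result, and its population should not be ambiguous.

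A third defence is that there may be few or no baseline-normal infants: Protocol 3.2.2.1 refers to hematological changes with the disease, and the escalation criteria in 3.1.1.1 include an ongoing transfusion requirement. That is plausible, but the documents do not establish it.

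A reader might go further and infer that the rule inflates the endpoint in the drug's favour, or that the restriction was removed on purpose. The documents support neither. They give no baseline hemoglobin counts. A baseline-normal infant who dies early, is transfused or becomes anemic can fail TFHN yet stay in the unrestricted denominator, which lowers the rate. Inflation may be the likelier direction, since staying normal is ordinarily easier than becoming normal, but that is reasoning and not a documented fact. SAP 13 records no deliberate change.

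**Conclusion.** The inconsistency is real and should be corrected. As written, Protocol 8.7 and SAP 9.1 can count infants with nothing to normalize, contrary to the synopsis.

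The size cannot be fixed from the documents. With 8 subjects, 1 to 4 baseline-normal infants who all meet TFHN, and about half of the others normalizing, the unrestricted rate is about 7 to 25 points higher. It is unchanged if there are no baseline-normal infants, and lower if those infants meet TFHN less often than the rest. A bias in favour of the drug is therefore possible, not shown. The primary endpoint, the sample size and the survival conclusions are unaffected.

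**What to change.** In SAP 9.1, restrict the TFHN numerator, denominator and time to TFHN to subjects in the Primary Efficacy Analysis Set with hemoglobin below the age-adjusted LLN at baseline. The synopsis says abnormal without defining it; this reading uses the same limit as the TFHN criteria. Make the matching edit in Protocol 8.7 at the next amendment. Protocol Section 11 requires protocol changes to go through an approved amendment, so the SAP clarification need not wait for it.

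Report baseline-normal infants under the maintenance endpoint. It is a different test, not a substitute: it requires no transfusions from Week 6 and no low values from Week 8 for at least 13 weeks.

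Before database lock, also decide how to classify, for this analysis, a baseline value that is normal only after a recent transfusion. The documents are silent on this. Applying the 2-week look-back of criterion 3 to the baseline value is one option, but the restriction does not depend on it.

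The cost is one SAP sentence and one programming flag. The denominator becomes smaller and the reported rate may be less favourable.
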